7.5 Definitions for Adverse Events and Serious Adverse Events^{ct.gov;eRsch}

Monitoring, Grading, Documentation, and Reporting of Adverse Events. *It is unlikely that the study protocol will lead to an adverse event (AE) or serious adverse event (SAE). However, we have established procedures for dealing with these events.* In the proposed study we will use the FDA definition of adverse events (AE) and serious adverse events (SAE). An adverse event is any undesirable experience, serious and non-serious, in a participant that may have a causal relationship with study participation. Symptoms or conditions present at or before the study that manifest themselves with the same intensity or frequency after study participation will not be recorded as adverse events. At the time of each contact, all participants will be monitored for the development of adverse experiences. Any concerns will be immediately reported to the PI who will review the information.

7.5.1 Relationship to Participation –

The PI will classify the relationship of the study protocol to the event as:

- *Definitely Not Study-Related:* There is a 0% chance the event is related to the study. It is clear that the participant's clinical state fully explained the event, and not the study protocol.
- *Possibly Study-Related:* There is a 1-49% chance the event is related to the study. The participant's clinical state can explain the event; however, the study protocol could possibly have influenced the event.
- *Probably Study-Related:* There is a 50-99% chance the event is study related. The event follows a reasonable temporal sequence associated with participating in the study and cannot be fully explained by the participant's clinical state.
- *Definitely Study-Related.* There is a 100% chance the event is study-related. The

event follows a reasonable temporal sequence associated with participating in the study and cannot be explained by the participant's clinical state.

7.5.2 Severity of Event

The scale below will be used to estimate the grade of severity of the adverse event:

- *Grade 1 Mild:* Transient or mild discomfort, no limitation of activity, no or minimal intervention/therapy required.
- *Grade 2 Moderate:* Mild to moderate limitation in activity; some assistance may be needed; no or minimal intervention/therapy required.
- Grade 3 Severe: Marked limitation in activity; some assistance usually required; intervention/therapy required; hospitalization possible.
- Grade 4 Life –threatening: Extreme limitation in activity; significant assistance required; significant intervention/therapy required; hospitalization probable (SAE)

7.5.3 Expectedness

Expected adverse events: Given that the population for this study consists of pre-operative patients experiencing varying levels of pre-operative risk, we expect morbidity or mortality from surgical complications, as well as serious and non-serious surgical complications at a rate consistent with the general surgical patient population. Study staff may become aware of these complications during review of medical charts, or from participant self-report during follow up assessments.

7.6 Safety Monitoring

Responsibility for Data and Safety Monitoring. The PI, [name], with assistance from the mentoring team, will be primarily responsible for monitoring participant safety. The primary concern will be the appropriate referral for patients who experience distress during assessment as well as the protection of client confidentiality. The PI will meet weekly with staff on the project, at which time they will evaluate the progress of the project, including issues regarding data management and participant risk. The PI will meet with mentors at monthly (e.g. [name]) to review study progress and any issues that arise. Urgent issues will be addressed immediately.

Data Management. Project staff will be educated on the latest policies regarding the ethical treatment of participants and the protection of confidentiality. Several procedures will be utilized to guarantee the validity, integrity, accuracy and completeness of the data. Data files are accessible only to project personnel and are password protected. Finally, the project database will also be password protected and accessible only to research staff. Files used in data analysis will not have any identifying information in them – just randomly assigned ID numbers. All identifying information will be kept in a separate password protected file. All paper data will be filed in locked cabinets inside locked rooms that only the PI and research staff will have access to. No patient identifiable information will be released or published without written permission unless

required to do so by law.

Entities conducting monitoring. The Michigan Medicine IRB (IRBMED) will review this protocol and all procedures and will provide oversight. Monitoring will be done by the PI, mentors, and IRBMED.

What is monitored? Monitoring is done of all procedures to ensure that they conform to approved protocol; of unforeseen circumstances that might arise and affect safety; of all reports of serious adverse events as defined in 38 CFR 46 (death, new prolonged hospitalization, persistent or significant disability/incapacity, or congenital anomaly/birth defect); of other significant adverse events (adverse events that lead to drop out by participant, termination by the investigator, termination or reduction of treatment); of unexpected adverse events resulting from the study; and of expected adverse events.

Data and Safety Monitoring Plan

Safety Monitoring

The Principal Investigator, [name], will ultimately be responsible for monitoring the data safety and quality of the study with involvement from the study coordinator. It should be noted that all research projects involving human participants, including the proposed one, require approval from the Institutional Review Board (IRBMED). A Certificate of Confidentiality will be provided for this study from the National Institute on Health (NIH).

[name] will ensure that all relevant IRB policies, procedures and stipulations are being followed. [name] also will be responsible for ensuring that project staff adhere to the IRB policies including: (1) all participants will understand, agree to, and sign a written consent form before participating; (2) strict adherence to a participant's right to withdraw or refuse to answer questions will be maintained; (3) the assessments will be completely confidential and no names will be associated with the assessment data; (4) consent forms and identifying information will be kept separately from the participant data; (5) all identifying information (consents, tracking data) will be kept locked at all times and computer files will have restricted access; (6) participants will be informed in writing in the consent form how to contact the PI, the project manager, and IRB office with any questions and/or concerns.

Crisis Assessment: [name] will be responsible for providing training to all research staff regarding procedures for identifying, managing, and responding appropriately to acute warning signs of distress that could occur as a result of the assessments. Such strategies include maintaining an empathic response, acknowledging the distress through reflection, and eliciting or encouraging use of relaxation and cognitive calming strategies. Study staff will receive training from [name] in crisis assessment and management procedures in the event that participants reveal suicidal or homicidal ideation, child physical/sexual abuse, or concerns about safety. These crisis procedures will include a review of the study protocol regarding the limits of confidentiality, how to liaison with study site staff (i.e., in-patient psychiatry, emergency department) to arrange for an assessment, circumstances

in which it may be necessary to notify authorities regarding intent to harm self or others (i.e. participant provider, child protective services), and the development of safety plans and resources. Study procedures also will include immediately paging/contacting [name] in cases in which this may become necessary (or contacting the assigned backup clinician during designated time periods). [name] will be responsible for providing regular supervision to research staff having direct contact with participants including crisis procedures for assessment and referral procedures for participants who meet criteria for suicidality. Supervision will focus on procedures for managing issues that could arise.

In the case that a participant indicates any level of suicidal ideation or recent attempt during encounters with any study staff a suicide risk management protocol will be used. The protocol utilizes an algorithm of scripted risk assessment questions and “action steps” dependent on the participant responses. Based on the level of risk determined by the algorithm, study staff may perform one or more of the following: a) recommend the participant call or be transferred to the national suicide crisis hotline, the University of Michigan’s Psychiatric Emergency Services (PES), or the nearest emergency department to immediately address suicide risk and determine whether emergency medical services or police should be activated to conduct a wellness check in the patient’s home or community, b) notify a designated on-call study team clinician when the suicide risk management algorithm has been activated, and when any questions arise regarding risk management.

Data Monitoring Plan

The Principal Investigator (PI) ultimately will be responsible for monitoring the data safety and quality with involvement from study coordinator. Data will be collected using the Qualtrics survey platform and or/standardized paper forms and will only be identified with the study ID of the participant. The codes that link the name of the participant and the study ID will be kept separately and securely, along with any signed consent forms obtained. Quality control and reliability of screening, baseline and follow-up assessments will be monitored by [name] throughout the trial via regular meetings and observation of the research staff conducting standardized assessments. Additional data will be stored in a study database created within the REDCap application. The quality of the data will be monitored throughout the study. Data will be analyzed using a data analysis program such as SAS software. Data quality will be monitored by random inspection of the completed forms by the research staff and any problems detected will be discussed with the PI.

Qualitative interviews will be conducted by trained research staff. The qualitative interviews will be audio-recorded. The audio-recordings of the sessions and interviews will be uploaded to a secure network server with restricted access. Once collected, participant data will remain confidential.

8 STATISTICAL CONSIDERATIONS^{ERSCH}

8.1 Sample Size

Sample Size and Power Considerations. The sample size ($N = 90$) was primarily chosen to facilitate conclusions regarding study feasibility, acceptability, and provide experience with study protocol (e.g. recruitment, retention, assessment, and analysis). Participant retention ($n = 72$; 80%) is achievable using methods utilized in mentor's past research^{27,28} and described in the retention section. A final sample of 72 participants will provide power of .80 to detect a medium effect ($f^2 = .20$) using the proposed analyses. Based on meta-analyses of MI for excessive drinking, medium effects are expected within a 4-month follow up period^{29,30}. Between group differences in post-operative morbidity, mortality, and healthcare utilization will likely be 'very small' based on base-rates of postoperative complications. This study is underpowered to detect small effects. For this reason, hypothesis testing is considered 'exploratory.' Therefore, this study will primarily provide pragmatic information and experience with the study protocol to inform a fully-powered RCT.

8.2 Data Analyses^{ct.gov}

8.2.1 General Approach

Data Preparation. Prior to analyses, we will examine patterns of missing data, research dropout, intervention fidelity, distributional properties of measures, correlations among outcome measures³¹. Given the small sample, we will pay particular attention to data distribution and use transformations when appropriate.

Data Analysis. We will examine between group effects on alcohol use using General Estimated Equations (GEE). We expect balanced groups on key variables as a result of urn randomization but will test the following covariates for systematic effects on outcome; gender, age, race/ethnicity, surgery type, and drug use. These analyses will use regression modeling using GEE due to the correlated structure of our data from repeated measures at baseline and follow-up. The GEE methodology properly estimates the regression coefficient and variance of the regression coefficient when correlated data are used in regression analysis will use all data available for participants including those subjects lost to attrition. Appropriate distributions will be used based on the nature and distribution of the response variable. Relevant covariates will be included such as gender, age, race/ethnicity, surgery type, smoking status, and drug use.

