3.2 Study flow

4 SELECTION AND ENROLLMENT OF PARTICIPANTS

4.1 Inclusion Criteria^{ct.gov;eRsch}

Patients will be eligible for participation if they are: 1) 18 - 75 years of age, 2) referred for elective or semi-elective surgery or pre-operative assessment in the next 120 days, and 3) Meet criteria for “risky drinking,” scoring ≥ 5 on the first 3-items of Alcohol Use Disorders Identification Test (AUDIT). These cutoffs are associated with increased rates of postoperative complications among pre-operative patients following elective surgeries.

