6 STUDY PROCEDURES^{ERSCH}

For Phase 3 we will conduct a randomized pilot trial test of Health Coaching and Brief Advice interventions to reduce alcohol use prior to elective surgery. The goal of the pilot trial is to assess the initial efficacy of Health Coaching relative to the Brief Advice Intervention and determine initial acceptability, feasibility, and fidelity of both conditions. Participants have a choice of intervention modality and they will either take place in-person or as a virtual meeting using an encrypted, university-supported virtual meeting platform. The in-person meetings will take place at either the Rachel Upjohn Building, in MCRU research space, or at a building within UM or UMHS, or a mutually agreed upon location within the community. If a participant cannot complete all study activities during one visit or virtual visit, we will allow participants to set an appointment to complete these activities within three days. This study has one baseline assessment. Follow-up surveys will take place at one-month post-baseline (Follow up 1; one week pre-surgery) and at four-months post-baseline (Follow-up 2; 3-months post-surgery).

Randomization

Participants will be urn randomized to study condition using computerized random number generator. Groups will be balanced based on gender.

Assessment and Measures

Baseline assessment will take place at least four weeks prior to surgery. The baseline assessment will take approximately 40 minutes to complete. Thus, the first appointment will take up to 120 minutes for those randomized to health coaching (15 minutes to

review the consent form; 40 minutes for baseline assessment; 50 minutes for the intervention; 10 minutes for the post-intervention feedback; and 5 minutes to provide the incentive) or 75 minutes for those assigned to receive brief advice (15 minutes to review the consent form; 40 minutes for baseline assessment; and 10 minutes for the brief advice intervention and 10 minutes for intervention feedback evaluation).

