6.2.3 Randomization and Retention

Computer-generated urn randomization²⁶ will ensure balanced groups based on gender. Research staff will be blind to participant study condition (with the exception of those delivering interventions). We will track participant retention as a measure of study feasibility. Retention strategies include, collecting multiple forms of participant and collateral contact information and sending reminders by e-mail, phone, and text. We aim to retain 80% of patients (72/90) using these strategies and those used in mentors' past research that achieved similar rates of retention.

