8.2.2 Primary Outcome

The primary outcome of this study is between group differences in change in alcohol use from baseline to follow-up. This is defined as change in average weekly alcohol use (quantity by frequency) as measured by the Time Line Follow Back. Our hypothesis is: Relative to the brief advice group, the health coaching group will experience greater reductions in average weekly alcohol use between baseline and follow-up. This

hypothesis is considered exploratory given the low power to detect significant differences.

Qualitative Analysis:

All qualitative interviews will be digitally audio-recorded and transcribed verbatim using a HIPAA-compliant transcription service. Transcripts and codes will be analyzed using Nvivo software. We will analyze data using applied thematic analysis. Emerging themes and data interpretations will be used for intervention refinement.

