9.3 Future Use of Stored Specimens and Data

9.4 Data Handling & Record Keeping

9.4.1 Quality Assurance & Quality Control

Throughout the proposed research investigation, participants' names and contact information will be stored in a secure, password-protected database, separate from their study data. Names will be linked to individual ID numbers *only* in a study database, which will be kept in a restricted access folder on a secure server. Patient audio from intervention sessions and exit surveys will also be kept in a restricted access folder on a secure server. All information collected will be accessible only to research staff who have completed and maintain mandatory training in the protection of human subjects (see 9.4.2)

REDCap will be used to track subject demographics, surgery details, screening scores, and level of study completion. REDCap uses several methods to protect data from vulnerability and exploitation. Incoming REDCap data gets filtered, sanitized and escaped as part of REDCap's security procedures. The study investigators will ensure that Research Assistants (RAs) and other study staff will only have access to the REDCap data and information they need to complete their work by creating and updating user rights in REDCap.

Qualtrics: The project-specific Qualtrics site is protected with a researcher-designated login name and password. The site houses the surveys and compiles data that staff will then transfer to a password protected Access database on the Department of Psychiatry secure network. For the web-based follow-up surveys, participants receive an email invitation inviting them to take the survey on-line and directing them to the Qualtrics site. An additional password may be given to participants in order for them to access to the site. There are systems in place that prevent the survey from being taken by the same user more than once. No identifying information is linked to the participants. There are security precautions in place to protect against unauthorized access, but there is a small risk of unauthorized access. Information regarding Qualtrics security and privacy statements can be found at <http://www.qualtrics.com/security-statement> and <http://www.qualtrics.com/privacy-statement>.

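### The urn balances on gender only, so the balance on key variables expected in section 8.2.1 does not extend to drinking severity, which the plan neither balances nor names as a covariate

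*Combined protocol and SAP*

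**What the plan says.** Section 8.2.1 (General Approach) credits the allocation method with balance on a set of variables it does not define: "We expect balanced groups on key variables as a result of urn randomization". The sentence goes on to say that certain covariates will be tested for effects on outcome.

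The two descriptions of the allocation agree with each other and are narrower. Section 6 (Randomization) says "Groups will be balanced based on gender". Section 6.2.3 says the urn "will ensure balanced groups based on gender". No other urn variable is named.

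A severity score exists before allocation. Section 4.1 makes patients eligible on "scoring ≥ 5 on the first 3-items of Alcohol Use Disorders Identification Test", and section 9.4.1 says "REDCap will be used to track subject demographics, surgery details, screening scores, and level of study completion".

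Section 8.2.2 describes the primary outcome as a between-group difference in change: "This is defined as change in average weekly alcohol use (quantity by frequency) as measured by the Time Line Follow Back".

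Section 8.2.1 has two covariate lists. Between them they cover gender, age, race or ethnicity, type of surgery, smoking and drug use. Neither names baseline drinking or the AUDIT score. Drug use does not stand in for it, because section 6 measures alcohol and drug use with separate instruments. Baseline drinking does enter the GEE as one of the repeated measures.

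**The concern.** The expectation in 8.2.1 is wider than the design can deliver. On any reading of key variables that goes beyond gender, balance comes only from ordinary randomisation in a small sample, apart from what gender happens to carry through its correlation with other variables.

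Drinking severity matters most because the endpoint is change in drinking. The arm that happens to start heavier will, on average, regress further towards the mean. A plain comparison of change would then credit part of that fall to the intervention, or hide a real effect if the heavier arm is Brief Advice. The plan has two places to deal with this, the allocation and the model, and names drinking severity in neither as a balancing factor or covariate.

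What is at stake is how the pilot's effect estimate is read when the fully powered trial is planned. The validity of the randomisation is not in question.

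**Working it through.** **Inputs from the documents.** Sections 1.2 and 8.1 give N = 90, 45 per arm, and 72 retained (80%).

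- Check: 72 / 0.80 = 90; 90 / 2 = 45; 72 / 2 = 36.
- The plan gives no figure for expected imbalance, so there is none to reproduce. The power statement in 8.1 is not used here.

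**Assumptions (not in the documents).** The baseline mean difference is approximately normal, baseline and follow-up SDs are equal, and the baseline-to-follow-up correlation rho is 0.3 to 0.7.

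**Step 1: size of chance imbalance.** For a variable outside the urn and uncorrelated with gender, the SE of the standardised baseline difference is sqrt(2/n).

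| Per arm | SE (SD units) | 95% range | P(above 0.25 SD) | P(above 0.30 SD) |
|---|---|---|---|---|
| 45 | sqrt(2/45) = 0.211 | ±0.41 | 23.6% | 15.5% |
| 36 | sqrt(2/36) = 0.236 | ±0.46 | 28.9% | 20.3% |

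The first row describes the arms as randomised and is the one to rely on. The second applies only to a comparison of completers.

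**Step 2: effect on a change contrast.** Let the arms differ by D at baseline. With equal SDs the follow-up difference carries rho × D of this, so the difference in change carries (rho − 1) × D. The shift has size (1 − rho) × D and favours the arm that started heavier. For D = 0.25 SD:

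- rho = 0.3: 0.7 × 0.25 = 0.175 SD
- rho = 0.5: 0.5 × 0.25 = 0.125 SD
- rho = 0.7: 0.3 × 0.25 = 0.075 SD

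**Step 3: what a severity factor in the urn would gain.** A simulation of 90 patients (6,000 runs) assumed an urn starting with one ball per arm and adding one of the opposite arm after each draw, half women, normal severity, and no link between gender and severity.

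| Urn | SD of severity imbalance | P(above 0.2 SD) | P(above 0.3 SD) |
|---|---|---|---|
| Gender only | 0.213 | 35% | 16% |
| Gender plus high/low severity | 0.163 | 22% | 7% |

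The first row agrees with the formula in step 1.

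That is the gain for the variable that is split. The AUDIT score is only a proxy for Timeline Followback drinking. If the two correlate r, the variance of the imbalance in weekly drinking is about r² × 0.163² + (1 − r²) × 0.213²:

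- r = 0.5: SD 0.202, P(above 0.25 SD) about 22%
- r = 0.8: SD 0.182, P(above 0.25 SD) about 17%

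Both compare with about 24% for the gender-only urn.

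**Step 4: what baseline adjustment would gain.** Adjusting follow-up for baseline removes the rho × D carried forward, so the shift in step 2 largely disappears. For one follow-up, in units of the outcome variance, the variance of change is 2 − 2·rho and the variance after adjustment is 1 − rho²:

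- rho = 0.5: 1.00 against 0.75, 25% lower
- rho = 0.7: 0.60 against 0.51, 15% lower

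**The case against.** The strongest reply is that randomisation already covers this. Over repeated allocations the change contrast is unbiased, and chance baseline differences are part of its standard error. That is correct. At 36 per arm the SE of the change contrast is sqrt(2 − 2·rho) × 0.236, or 0.236 SD at rho = 0.5 and 0.183 SD at rho = 0.7. Shifts of 0.125 and 0.075 SD are therefore about half and two fifths of one SE. A reader might infer that the randomisation is biased or defective; the documents do not support that. They describe a computer-generated urn, and using gender as its only factor is a legitimate choice in a 90-patient pilot.

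Second, the plan does not rest on balance alone. It tests covariates, leaves its final list open, allows transformations, and has baseline as a repeated measure. So it would be wrong to say that baseline drinking is ignored. But a repeated-measures model with a free group difference at baseline yields exactly the change contrast of step 2, and the plan does not specify a form that avoids it. An open list does not prespecify the covariate that matters most.

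Third, 8.1 and 8.2.2 call hypothesis testing exploratory, and 8.1 says the sample size was chosen mainly for feasibility and acceptability. No confirmatory conclusion depends on severity balance. This stands, and it limits the weight of the point.

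Fourth, changing the urn does little. By step 3 that is fair, so the urn should not be the main remedy.

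**Conclusion.** The point holds in a limited form. Section 8.2.1 claims a balance that sections 6 and 6.2.3 deliver for gender only. Drinking severity, measured before allocation and closest to the primary outcome, is absent from the urn and from both covariate lists. The chance of a baseline difference above 0.25 SD is about 24% with 45 per arm, and such a difference would move a plain change contrast by 0.075 to 0.175 SD for rho between 0.7 and 0.3.

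These figures assume approximate normality of the mean difference, equal SDs at baseline and follow-up, and no correlation between gender and severity. If the follow-up SD is smaller than the baseline SD, the shift is larger. If gender and severity are correlated, the imbalance is somewhat smaller.

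Two stronger conclusions are tempting and should not be drawn: that the treatment comparison is biased by design, and that adding AUDIT to the urn would solve the problem. The first mistakes chance imbalance for bias; the second overrates a banded proxy. The severity is modest.

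**What to change.** 1. **Section 8.2.1, wording.** State that the urn is expected to balance only the variables entered into it. This costs one sentence.

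2. **Sections 6 and 6.2.3, allocation.** For patients not yet randomised, add the screening three-item AUDIT score in two bands, with the cut fixed in advance, alongside gender. The score is already collected, so the cost is one more input to the randomisation program and a short amendment. The gain is modest (step 3), and there is none for patients already allocated. The protocol summary plans a start in March 2019 and a duration of two years and four months, so enrolment may be complete.

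3. **Section 8.2.1, model.** Whether or not enrolment is complete, prespecify one of two forms before the analysis:
   - GEE for the follow-up values, with baseline Timeline Followback weekly drinking as a covariate on the scale used for the outcome; or
   - GEE for all visits with baseline means constrained to be equal across arms. This adjusts for baseline only if the working correlation allows for dependence between visits; an independence structure would not.

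   The first is simpler but leaves out patients with no follow-up value, while the second keeps their baseline records. Either removes most of the effect of an imbalance and improves precision (step 4). The covariate form costs one model term; the constrained form adds none.
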